2.4.2 Justification for Selection of Doses/Timing of Investigational Product

The route of administration and the dosage regimen of 60 mg/kg body weight once weekly IV of Liquid Alpha₁-PI (Human) is recommended for chronic augmentation and maintenance therapy in adults with clinical evidence of emphysema due to severe AAT deficiency (e.g., phenotypes PiZZ, PiZ [null], Pi [null] [null]; PiSZ) (Prolastin-C Liquid- alpha₁-proteinase inhibitor [human] injection, solution [US prescribing information, 2020](#)).

Augmentation therapy with weekly IV infusions of 60 mg/kg AAT may be sufficient to slow progression of lung density decline in patients with AATD patients ([Dirksen 2009](#)); however, other dosing regimens have been also widely used: 120 mg/kg every 2 weeks, 180 mg/kg every 3 weeks, 250 mg/kg once a month ([Stoller 2003](#); [Miravitles 1999](#), [Vidal 1995](#)). The safety profile of AAT has not been modified according to the dosing regimen, and there has been no indication of any dose-dependent toxicity in AAT deficient subjects. AAT is a normal constituent of human plasma, which does not contribute significantly to plasma osmolality, and suffers no appreciable glomerular filtration.

Higher doses than 60 mg/kg at weekly intervals have been well tolerated with no safety issues. Campos and colleagues evaluated weekly doses of 120 mg/kg in patients with AATD which had the salutary effect of bringing AAT levels to within the normal range and improvement in biomarkers ([Campos 2019](#)). In the SPARK clinical study in subjects with AATD, weekly doses of 120 mg/kg alpha₁-PI resulted in an average steady state mean trough concentration of AAT (27.7 μ M) that was within the reported normal range of AAT serum levels (20 to 53 μ M) in non-AATD individuals. The SPARK study was conducted by Grifols to assess the safety and PK of weekly IV infusions of alpha₁-PI at 120 mg/kg compared to the approved (product labeling) dose of 60 mg/kg in 30 subjects. In this study, a total of 30 subjects received weekly doses of 120 mg/kg for 8 weeks, and the results demonstrated that alpha₁-PI, was also safe and well-tolerated at this dose ([Campos 2013](#)). Additionally, Grifols is currently investigating the efficacy of 60 mg/kg and 120 mg/kg alpha₁-PI using CT densitometry as the primary efficacy endpoint in a randomized, placebo-controlled trial in subjects with pulmonary emphysema due to AATD; safety and tolerability of the 120 mg/kg/week dose has been good in this ongoing clinical trial. Data from an additional proof-of-concept study in 75 subjects with new onset type 1 diabetes mellitus (T1DM) with residual β cell function evaluated the safety and potential therapeutic

GRIFOLS Bioscience Industrial Group	Number	BIG-CL-PRT-000019	Version	6.0	Status	Effective	Effective Date	08-Dec-2021	Page	31 of 94
	GC2006-A Multicenter, Randomized, Open-label, Parallel Group Pilot Study to Evaluate the Safety and Efficacy of Prostasin®-CL Liquid plus Standard Medical Treatment (SMT) versus SMT alone in Hospitalized Subjects with COVID-19									

effect of weekly 90 mg/kg and 180 mg/kg alpha₁-PI for 13 or 26 weeks. This study (GTI1302) showed that both doses were well-tolerated, however it was not powered adequately to demonstrate efficacy of alpha₁-PI at Week 52, and additional data would not change the outcome, so for reasons of futility the study was discontinued. However, safety of all doses (including weekly alpha₁-PI at 180 mg/kg) was shown.

Subjects randomized to combination with SMT will receive 2 doses of 120 mg/kg of Liquid Alpha₁-PI (Human) administered with the first infused on Day 1 and the second on Day 8.

2.5 Compliance Statement

This study will be conducted under the conditions described in this protocol and in compliance with the International Council for Harmonisation of Technical Requirements for Pharmaceuticals for Human Use (ICH) Good Clinical Practice (GCP) and all applicable regulatory requirements.

2.6 Study Population

The purpose of this study is to determine if Liquid Alpha₁-PI (Human) plus SMT can reduce the proportion of subjects dying or requiring intensive care unit (ICU) admission on or before Day 29 or who are dependent on high flow oxygen devices or invasive mechanical ventilation on Day 29 versus placebo plus SMT in hospitalized subjects with COVID-19.

Approximately 100 subjects will be randomized (1:1) with an interim analysis after 50 subjects (approximately 25 per group). There will be no interruption in study conduct during interim analysis as this simply represents sponsor safety due diligence during the COVID-19 pandemic.

Interim Futility Analysis: An interim futility analysis will be conducted to assess whether the trial will be terminated due to lack of efficacy (futility) based on all available data assessable for the primary endpoint and key secondary efficacy endpoints.

2.7 Relevant Data and Literature Review

2.7.1 COVID-19 Therapeutic Approaches

Coronaviruses (CoVs) typically affect the respiratory tract of mammals, including humans, and lead to mild to severe respiratory tract infections. In the past two decades, two highly pathogenic human CoVs (HCoVs), including severe acute respiratory syndrome coronavirus (SARS-CoV) and Middle East respiratory syndrome coronavirus (MERS-CoV), emerging from animal reservoirs, have led to global epidemics with high morbidity and mortality.

Several studies demonstrate that cells infected by SARS-CoV produce elevated levels of pro-inflammatory cytokines (PICs) in order to combat the invading viruses. However, the overproduced PICs (including monocyte chemoattractant protein-1 [MCP-1], transforming growth factor β 1 [TGF- β 1], tumor necrosis factor- α [TNF- α], interleukins- 1 β and -6 [IL-1 β , and IL-6]), may cause immuno-mediated damage to the lungs and other organs, resulting in acute lung injury (ALI) and ARDS (He 2006; DeDiego 2014).

GRIFOLS Bioscience Industrial Group	Number	BIG-CL-PRT-000019	Version	6.0	Status	Effective	Effective Date	08-Dec-2021	Page	32 of 94
	GC2006 -A Multicenter, Randomized, Open-label, Parallel Group Pilot Study to Evaluate the Safety and Efficacy of Prolastin®-CLiquid plus Standard Medical Treatment (SMT) versus SMT alone in Hospitalized Subjects with COVID-19									

The elevated levels of PICs in blood released from the SARS-CoV-infected cells and the uninfected cells stimulated by viral antigens or some PIC-regulatory factors, e.g. Nuclear Factor-kappaB (NF-κB) and p38 (a mitogen-activated protein kinase) (He 2006; DeDiego 2014), may damage the cells in the lungs and other organs. In addition, blood hypo-oxygenation due to ARDS and disseminated intravascular coagulation resulting from impairment of microvessel endothelial cells may further damage the structure and function of different organs in SARS patients, resulting in multi-organ dysfunction.

The ACE2 expressing cells are the primary targets for SARS-CoV infection in vivo humans initiating a massive cascade of pro-inflammatory cytokines via macrophages over-activation causing ARDS. High levels of PICs are expressed in the SARS-CoV-infected ACE2+ cells, but not in the uninfected cells (He et al., 2006).

Therefore, application of PIC antagonists may reduce the severity and mortality of SARS and may potentially reduce other pathogenic human coronaviruses (He 2006; DeDiego 2014; Tse 2004). In the current study it is considered that the modulatory and anti-inflammatory properties of Liquid Alpha₁-PI (Human) may attenuate the deleterious effects of cytokine release syndrome engendered in COVID-19.

Currently, there are no approved treatments for COVID-19 in Europe or the United States. The lack of disease-directed therapeutic options has led to urgent interventions in anticipation of some potentially promising effects. Some antivirals are currently under evaluation. These include favipiravir (AVIGAN) manufactured by Fujifilm in Japan, Gilead's remdesivir, and Kaletra® (lopinavir/ritonavir) commercially available for human immunodeficiency virus (HIV). Although Kaletra® did not show demonstrable efficacy in a recently reported study in China (Cao et al., 2020), additional trials are underway. There are also investigations of chloroquine and hydroxychloroquine as treatment modalities and potential applications for post-exposure prophylaxis according to Clinicaltrials.gov and other clinical trial registries. These and other potential therapeutic agents are described on the World Health Organization (WHO) website file: [WHO Landscape Therapeutics under investigation 17 Feb 2020.pdf](#) (accessed 19 March 2020).

To date there are no confirmed specific disease modifying agents. Therefore, the potential therapeutic benefit conveyed by the immunomodulatory effects of Liquid Alpha₁-PI (Human) warrants clinical investigation. This is particularly true given the urgency and extent of the COVID-19 pandemic.

3 STUDY OBJECTIVES AND PURPOSE

3.1 Efficacy Objectives

3.1.1 Primary Efficacy Objective

To determine if Liquid Alpha₁-PI (Human) plus SMT can reduce the proportion of subjects dying or requiring intensive care unit (ICU) admission on or before Day 29 or who are dependent on high flow oxygen devices or invasive mechanical ventilation on Day 29 versus placebo plus SMT in hospitalized subjects with COVID-19.

GRIFOLS Bioscience Industrial Group	Number	BIG-CL-PRT-000019	Version	6.0	Status	Effective	Effective Date	08-Dec-2021	Page	33 of 94
	GC2006 -A Multicenter, Randomized, Open-label, Parallel Group Pilot Study to Evaluate the Safety and Efficacy of Prostasin®-CL Liquid plus Standard Medical Treatment (SMT) versus SMT alone in Hospitalized Subjects with COVID-19.									

3.1.2 Secondary Efficacy Objective

To compare Liquid Alpha₁-PI (Human) plus SMT versus placebo plus SMT with regard to clinical efficacy as assessed by clinical severity, duration of hospital stay, dependency on oxygen or new need for ventilatory support, clinical response criteria including National Early Warning Score (NEWS), and clinical status scale through Day 29 in hospitalized subjects with COVID-19.

3.1.3 Exploratory Efficacy Objectives

- To evaluate the effect of Liquid Alpha₁-PI (Human) plus SMT versus placebo plus SMT with regard to quantitative severe acute respiratory syndrome, coronavirus 2 (SARS-CoV-2) viral load and anti-SARS-CoV-2 antibodies in hospitalized subjects with COVID-19.
- To evaluate whether Liquid Alpha₁-PI (Human) plus SMT versus placebo plus SMT reduces the frequency of hyperinflammation based on a pre-specified biochemical definition through Day 29.
- To evaluate cytokine profile changes from baseline Liquid Alpha₁-PI (Human) plus SMT versus placebo plus SMT through Day 29.
- To evaluate levels of alpha 1-PI (AAT) activity and antigen through Day 29

3.2 Safety Objective

To determine the safety and tolerability profile through Day 29 of Liquid Alpha₁-PI (Human) plus SMT versus placebo plus SMT in hospitalized subjects with COVID-19.

4 STUDY DESIGN

4.1 Primary Endpoint and Secondary Endpoints

4.1.1 Primary Efficacy Endpoint

The primary efficacy endpoint is the proportion of subjects dying or requiring ICU admission on or before Day 29 or who are dependent on high flow oxygen devices or invasive mechanical ventilation on Day 29.

4.1.2 Secondary Efficacy Endpoints

Secondary efficacy endpoints include the following:

- Assessment of Clinical Severity: Change in NEWS from baseline (Day 1 through Day 29) The NEWS has demonstrated an ability to discriminate patients at risk of poor outcomes. This score is based on 7 clinical parameters (respiration rate, oxygen saturation, any supplemental oxygen, temperature, systolic blood pressure, heart rate, level of consciousness [Alert, Voice, Pain, Unresponsive]). <https://www.mdcalc.com/national-early-warning-score-news> (Appendix 2)

GRIFOLS Bioscience Industrial Group	Number	BIG-CL-PRT-000019	Version	6.0	Status	Effective	Effective Date	08-Dec-2021
	GC2006 -A Multicenter, Randomized, Open-label, Parallel Group Pilot Study to Evaluate the Safety and Efficacy of Prolastin®-CL Liquid plus Standard Medical Treatment (SMT) versus SMT alone in Hospitalized Subjects with COVID-19						Page	35 of 94

- Proportion of subjects with evidence of hyperinflammation on Day 1, Day 5, Day 15, and Day 29 defined as:
 - a) Lymphocyte counts <1000 cells/ μ L, AND
 - b) Two of the following 4 criteria:
 - i) Ferritin > 500ng/mL,
 - ii) LDH > 300 U/L,
 - iii) D-Dimers > 1000 ng/mL (fibrinogen equivalent units [FEU]) or > 2 times upper normal limit,
 - iv) C-reactive protein (CRP) > 70 mg/L
- Change from baseline in cytokine profile (cytokine panel includes IL-1 β , IL-10, IL-6, IL-8, IL-2, interferon γ , and tumor necrosis factor- α [TNF- α]) to Day 5 \pm 1 day, Day 15 \pm 1 day, and Day 29 \pm 1 day
- Change from baseline in levels of alpha 1-PI (AAT) activity and antigen through Day 29 (both plasma [sodium citrate] and serum samples to be stored for measurement of both antigenic content and functional activity [potency])

4.1.4 Safety Endpoints

The safety endpoints include:

- Cumulative incidence of treatment-emergent serious adverse events (SAEs) and potentially related SAEs through Day 90 phone check
- Cumulative incidence of Grade 3-5 treatment-emergent adverse events (TEAEs) and potentially related severe TEAEs through Day 29 as defined in the Common Terminology Criteria for Adverse Events (CTCAE), US Department of Health and Human Services, National Institutes of Health (NIH), and National Cancer Institute (NCI)
- Cumulative incidence of all TEAEs and potentially related TEAEs through Day 29

In this clinical study, disease progression is defined as the worsening of a subject's condition attributable to the disease for which the investigational product is being studied. It may be an increase in the severity of the targeted disease and/or increases in the symptoms of the targeted disease. Anticipated symptoms of COVID-19 include fever, cough, hypoxia, dyspnea, hemoptysis, myalgia, fatigue, pharyngitis, which may develop at any time during the course of the disease. The development of COVID-19 symptoms during the clinical study should not be recorded as individual TEAEs, unless there is evidence suggesting a causal relationship between blinded Liquid Alpha₁-PI (Human)/Placebo and the TEAE.

4.2 Study Design and Plan

This is a prospective, multi-center, randomized (1:1), double-blind, placebo-controlled study of Liquid Alpha₁-PI (Human) plus SMT versus placebo plus SMT in subjects with COVID-19 who are hospitalized. The first 6 subjects randomized will be staggered, so randomization is no closer than 1 week apart. If there are no definitely related serious adverse events (SAEs) reported by the time Day 8 is completed by the 6th subject, competitive enrollment would ensue thereafter. If a definitely related SAE were to be reported among these 6 subjects, and the subject was found by

GRIFOLS Bioscience Industrial Group	Number	BIG-CL-PRT-000019	Version	6.0	Status	Effective	Effective Date	08-Dec-2021
	GC2006 -A Multicenter, Randomized, Open-label, Parallel Group Pilot Study to Evaluate the Safety and Efficacy of Prolastin®-C Liquid plus Standard Medical Treatment (SMT) versus SMT alone in Hospitalized Subjects with						Page	36 of 94

the Study-Independent Safety Review Committee (SISRC) to be randomized to the Liquid Alpha₁-PI (Human) plus SMT arm, the SISRC would carefully review and evaluate the case and make appropriate recommendations with regard to study status.

In this study, symptomatic subjects with positive polymerase chain reaction (PCR; reverse transcriptase [RT]-PCR) or nucleic acid amplification technology (NAT) for SARS-CoV-2 (or other commercial or public health assay approved by regulatory authorities) will receive placebo plus SMT *or* SMT plus Liquid Alpha₁-PI (Human) given as two intravenous (IV) doses of 120 mg/kg (body weight) one week apart (on Day 1 and Day 8); if the subject is discharged from the hospital then the 2nd infusion is not mandatory, and is at the discretion of the Principal Investigator and subject.

Specifically, subjects randomized to combination Liquid Alpha₁-PI (Human) will receive the first IV infusion of blinded Liquid Alpha₁-PI (Human) (120 mg/kg body weight) or Placebo on Day 1. A second Placebo/ Liquid Alpha₁-PI (Human) dose of 120 mg/kg body weight will be administered a week later on Day 8. If the subject has been discharged from the hospital at the time of the Day 8 blinded Placebo/Liquid Alpha₁-PI (Human) infusion, the 2nd infusion is not mandatory, and is at the discretion of the Principal Investigator and subject.

Approximately 100 subjects will be randomized (1:1) with an interim analysis after 50 subjects (approximately 25 per group). There will be no interruption in study conduct during interim analysis as this simply represents sponsor safety due diligence during the COVID-19 pandemic. Interim Futility Analysis: An interim futility analysis will be conducted to assess whether the trial will be terminated due to lack of efficacy (futility) based on all available data assessable for the primary endpoint and key secondary efficacy endpoints.

All subjects will be followed daily through Day 10 (note: for Day 6 through Day 10, this stipulation is for as long as subjects are hospitalized). After Day 6, if subjects are discharged from the hospital, evaluations at Day 15 and 29 are required. Berlin criteria for ARDS ([Appendix 3](#)) will be assessed on Day 1, 5, 15, and 29. Subjects remaining hospitalized will be followed daily through Day 29. Phone Checks will occur at Day 60 and Day 90 for vital status (living or deceased), any hospital re-admissions or serious/non-serious adverse events after the Day 29 Final Clinic Visit. Details are provided in [Appendix 1](#) (Schedule of Study Procedures). Clinical status will be evaluated for all hospitalized subjects daily with vital signs, Ordinal Scale (7 categories analogous to Cao et al. 2020), and NEWS at Screening/Baseline and during Liquid Alpha₁-PI (Human) plus SMT or placebo plus SMT treatment and during Follow-up. The NEWS calculation is delineated in [Appendix 2](#) and can be calculated using the on-line web tool at <https://www.mdcalc.com/national-early-warning-score-news>.

For all subjects, all laboratory samples must be drawn prior to infusion of Placebo/Liquid Alpha₁-PI (Human), if laboratory assessments are required for a day in which Placebo/Liquid Alpha₁-PI (Human) is being infused.

Respiratory samples for quantitative measurement of SARS-CoV-2 viral load by NAT or PCR (real-time RT-PCR) will be obtained on Day 1, and subsequently on Day 5± 1 day, Day 15± 1 day, and Day 29 ± 1 day (obtained via nasopharyngeal swab). The results of these samples are not necessary for continuing on study. Similarly, blood samples for quantitative measurement of

GRIFOLS Bioscience Industrial Group	Number	BIG-CL-PRT-000019	Version	6.0	Status	Effective	Effective Date	08-Dec-2021
	GC2006-A Multicenter, Randomized, Open-label, Parallel Group Pilot Study to Evaluate the Safety and Efficacy of Prolastin®-C Liquid plus Standard Medical Treatment (SMT) versus SMT alone in Hospitalized Subjects with						Page	37 of 94

IgM and IgG antibodies to SARS-CoV-2 via enzyme linked immunosorbent assay (ELISA), Indirect Fluorescent Antibody (IFA) or other assay methodology will be drawn at the same time points: Day 1, and subsequently on Day 5± 1 day, Day 15± 1 day, and Day 29 ± 1 day. The results of these samples are not necessary for continuing on study.

[figure not shown]
Ferritin, D-dimer, CRP and Basic chemistry analytes (creatinine, albumin, alanine aminotransferase [ALT], total bilirubin, lactate dehydrogenase [LDH]) will be assessed on Day 1 and on Day 5± 1 day, Day 15± 1 day, and Day 29 ± 1 day. An estimated glomerular filtration rate (eGFR) will also be calculated at these time points using the Cockcroft-Gault formula. Hematology (hemoglobin, hematocrit, platelet count, absolute neutrophil & lymphocyte count, leukocyte count with differential) will be assessed Day 5± 1 day, Day 15± 1 day, and Day 29± 1 day. All routine laboratory tests will be assessed locally at the hospital/site's laboratory. A cytokine panel will be performed at the same time points. Cytokine panel includes IL-1 β , IL-10, IL-6, IL-8, IL-2, interferon γ , and TNF- α . Note: serum samples must be stored at -70° C for later analysis at a reference laboratory. Levels of alpha 1-PI (AAT) activity and antigen will be evaluated on Day 1, on Day 8± 1 day, Day 15± 1 day, and Day 29 ± 1 day; both plasma (sodium citrate) and serum samples to be stored at - 70° C for measurement of both antigenic content and functional activity (potency) (all samples are mandatory at all time points regardless of hospital discharge status, except for the Day 8 AAT activity and antigen which is not required if subjects are discharged from the hospital and no 2nd blinded study drug infusion is administered).

This clinical trial will consist of the following phases:

- Screening/Baseline (Day 1) during which eligibility criteria are reviewed. Once all eligibility criteria are met and all pre-infusion assessments are completed, blinded Liquid Alpha₁-PI (Human) or Placebo administration can begin as expeditiously as feasible. On Day 8 a second IV dose of blinded Liquid Alpha₁-PI (Human) or Placebo will be administered on Day 8. If the subject has been discharged from the hospital at the time of the Day 8 blinded Liquid Alpha₁-PI (Human) or Placebo infusion, the 2nd infusion is not mandatory, and is at the discretion of the Principal Investigator and subject.
- SMT, Observations, and Follow-up (Days 2 to Day 29): SMT will be provided to all subjects with daily assessments while hospitalized and follow-up from Day 2 through Day 29±1 day (inclusive).
- Phone Checks will occur at Day 60 and Day 90 for vital status (living or deceased), any hospital re-admissions or serious/non-serious adverse events after the Day 29 Final Clinic Visit.

The overall study schema is shown in [Figure 4-1](#).

GRIFOLS	Number	BIG-CL-PRT-000019	Version	6.0	Status	Effective	Effective Date	08-Dec-2021
	GC2006 -A Multicenter, Randomized, Open-label, Parallel Group Pilot Study to Evaluate the Safety and Efficacy of Prolastin®-C Liquid plus Standard Medical Treatment (SMT) versus Bioscience Industrial Group							
								38 of 94

IV = intravenous; SMT = standard medical treatment

*Note: If the subject has been discharged from the hospital at the time of the Day 8 blinded Liquid Alpha-1 PI infusion, the 2nd infusion is not mandatory, and is at the discretion of the Principal Investigator and subject

Figure 4-1 Overall Study Schema

GRIFOLS Bioscience Industrial Group	Number	BIG-CL-PRT-000019	Version	6.0	Status	Effective	Effective Date	08-Dec-2021
	GC2006 -A Multicenter, Randomized, Open-label, Parallel Group Pilot Study to Evaluate the Safety and Efficacy of Prolastin®-C Liquid plus Standard Medical Treatment (SMT) versus SMT alone in Hospitalized Subjects with						Page	39 of 94

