- to record any SAEs/non-serious AEs after the Day 29 Final Clinic Visit

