8.3.8 Adverse Event Documentation

All AEs and SAEs occurring on Day 1 through the Day 29 (± 1 day)/Final Visit must be fully recorded in the subject's medical record and CRF, and paper SAE report form (if serious).

At the time of the Day 60 (± 2 days) and Day 90 (± 2 days) Phone Checks any additional SAEs/non-serious AEs will also be collected and recorded.

It is the responsibility of the investigator to ensure that AEs are appropriately recorded.

AEs will be collected through directly observed events or spontaneously volunteered by the subject. Clearly related signs, symptoms and abnormal diagnostic procedures should preferably be grouped together and recorded as a single diagnosis or syndrome wherever possible.

The following variables must be recorded:

- The verbatim term (a diagnosis is preferred)
- Date/time of onset
- Date/time of resolution
- Severity (mild, moderate, severe [Grade 3 to Grade 5])
- Causality (unrelated, possibly related, definitely related)*
- Seriousness (yes, no)
- Action taken (with regard to IP)
- Other action (to treat the event)
- Outcome and sequel (follow-up on AE)

*Causality assessment will be made only when the AE occurs after the subject has initiated at least one infusion of the IP. An AE occurring before subject's exposure to IP will be always labeled as "unrelated".

For AEs that occur during infusions, the infusion rate in effect at the time of onset of the AE, the time of onset of the AE and the time of AE change materially in intensity and/or resolve will be captured.

In addition to the investigator's own description of the AE, each AE will be encoded according to the Medical Dictionary for Regulatory Activities (MedDRA).

For example, a laboratory test abnormality considered clinically significant, eg, causing the subject to withdraw from the study, requiring treatment or causing apparent clinical manifestations, or judged clinically significant in the context of the subject's medical history by the investigator, should be reported as an AE. Each event must be described in detail along with start and stop dates, severity, relationship to IP, action taken and outcome. Each

event must be adequately supported by documentation as it appears in the subject's medical or case file.

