- i. During study infusions on Day 1 and Day 8 vital signs will be measured immediately before the start of infusion, after the first 5 minutes of infusion, and subsequently at 5-10-minute intervals during infusion until the end of infusion. Vital signs will also be measured 2 hours after the end of study infusion.
- j. Day 8 AAT measurement for activity and antigen is only required if subject is in hospital.
- k. If the patient has been discharged from the hospital at the time of the Day 8 blinded Liquid Alpha₁-PI (Human) or Placebo infusion, the 2nd infusion is not mandatory, and is at the discretion of the Principal Investigator and subject
- l. Only applicable if subject remains hospitalized, except for Day 5 when all assessments are mandatory for all subjects.
- m. Mandatory even if subject has been discharged from hospital

Note: For assessment for early withdrawal see Section [5.3.4](#).

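### Adverse events are collected only if observed or volunteered, and scheduled contact drops from daily to a few visits at discharge, so an arm discharged sooner may appear to have fewer TEAEs

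*Protocol*

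**What the plan says.** **How events are collected.** Protocol 8.3.8 states: "AEs will be collected through directly observed events or spontaneously volunteered by the subject". No AE question, checklist or diary is specified. The reporting period is the same for everyone: "All AEs and SAEs occurring on Day 1 through the Day 29" visit must be recorded.

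**How often subjects are seen.** Section 4.2 says of inpatients: "Subjects remaining hospitalized will be followed daily through Day 29". For the others it says: "After Day 6, if subjects are discharged from the hospital, evaluations at Day 15 and 29 are required". Appendix 1, footnote l, says of the daily evaluations: "Only applicable if subject remains hospitalized, except for Day 5 when all assessments are mandatory for all subjects". Footnote m makes Days 5, 15 and 29 mandatory after discharge. The Day 8 infusion adds a contact only if the discharged subject takes it, because "the 2nd infusion is not mandatory, and is at the discretion of the Principal Investigator and subject". The Day 60 and Day 90 calls in Section 7.2.8 serve "to record any SAEs/non-serious AEs after the Day 29 Final Clinic Visit", so they are not aimed at Days 1 to 29.

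**An inconsistency.** Section 4.2 also says "All subjects will be followed daily through Day 10", with a note limiting Days 6 to 10 to inpatients. Read literally, Days 1 to 5 are daily for all subjects. Footnote l and the title of Section 7.2.3 make only Day 5 mandatory after discharge.

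**How events are summarised.** SAP 7.2.5 gives, by arm, the number and percentage of subjects with each type of TEAE, and total episodes in the overall table. Neither is adjusted for time in hospital or number of contacts. SAP 7 rules out formal testing. SAP 8.1 applies the same methods at the interim safety analysis.

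**The concern.** With a rule of observation or spontaneous report, the chance that an event is recorded depends on how often staff see the subject. That depends on length of stay, which treatment may change: time to hospital discharge is a secondary efficacy endpoint. Randomisation and blinding balance the arms at entry but do not equalise contact afterwards. If detection at home is lower and one arm leaves hospital sooner, that arm records fewer events even when the true risk is equal. A drug that shortens stay would look safer than it is, and one that lengthens stay would look less safe.

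The safety objective compares active treatment with placebo, so readers will set the by-arm TEAE percentages side by side whether or not a p-value is attached. Neither document mentions unequal ascertainment after discharge.

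**Working it through.** The plan gives no AE rate, detection rate or expected length of stay, so it has no figure to reproduce. Two checks are possible: a count of scheduled contacts, which comes from the documents, and an illustration of size, which rests on assumptions.

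**1. Scheduled contacts, Days 1 to 29.** For last hospital day D, contacts are the union of Days 1 to D with Days 5, 15 and 29 (Appendix 1, nominal days, without the optional Day 8 visit).

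| Last hospital day | Contacts in total | Of which after discharge |
|---|---|---|
| 3 | 6 | 3 (Days 5, 15, 29) |
| 4 | 7 | 3 |
| 5 | 7 | 2 (Days 15, 29) |
| 7 | 9 | 2 |
| 10 | 12 | 2 |
| 14 | 16 | 2 |
| 20 | 21 | 1 (Day 29) |
| 29 | 29 | 0 |

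Anyone discharged by Day 15 has a longest gap of 29 − 15 = 14 days, against 1 day for an inpatient. A discharged subject who takes the Day 8 infusion is observed until 2 hours after it. The next scheduled contact is Day 15, 7 days later.

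**2. Subjects with at least one recorded TEAE (the SAP's main summary).** Assumptions: the same true 29-day risk R in both arms (30%, 50% or 70%), detection 1 in hospital and q after discharge, and discharge on Day 7 against Day 10, or Day 6 against Day 12.

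With constant hazard λ = −ln(1 − R)/29, the recorded proportion is 1 − exp{−λ[D + q(29 − D)]}.

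Worked case: R = 50% gives λ = 0.0239. With q = 0.5, effective days are 7 + 0.5 × 22 = 18.0 against 10 + 0.5 × 19 = 19.5. Recorded proportions are 35.0% and 37.3%, a spurious gap of 2.3 points.

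Gap in percentage points (later-discharged arm minus earlier-discharged arm), range over R:

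| q | Day 7 v 10 | Day 6 v 12 |
|---|---|---|
| 1.0 | 0 | 0 |
| 0.8 | 0.5–0.9 | 1.1–1.8 |
| 0.5 | 1.5–2.9 | 2.9–5.7 |
| 0.3 | 2.2–4.7 | 4.3–9.4 |

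If 80% of the hazard falls in Days 1 to 7, the gaps for q from 0.8 to 0.3 shrink to 0.1–0.8 points (Day 7 v 10) and 0.8–4.9 points (Day 6 v 12).

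Over the two hazard shapes there are 36 scenarios with q < 1. Of these, 13 give under 1 point, 15 give 1 to 4 points and 8 give more than 4. The median is 1.7.

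**3. Episode totals (the SAP's overall table).** Expected recorded episodes are proportional to D × d_in + (29 − D) × d_out. With assumed detection of 0.9 in hospital and 0.5 at home:

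- Mean stay 8 v 10 days: (7.2 + 10.5)/(9.0 + 9.5) = 17.7/18.5 = 0.96.
- Mean stay 7 v 12 days: (6.3 + 11.0)/(10.8 + 8.5) = 17.3/19.3 = 0.90.

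These ratios describe episode counts. For subjects with at least one TEAE, the same inputs with R from 30% to 90% give 0.96–0.98 (0.8–1.6 points) and 0.91–0.95 (2.0–3.9 points).

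**The case against.** **Contacts are not the reporting period.** Events with onset on any of Days 1 to 29 are recordable, with dates, at the next visit. This stands. A reader might infer from the contact table that events at home go uncollected, and the documents do not support that. What is exposed is the event that the subject does not volunteer, after a gap of up to 14 days.

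**Subjects may in fact be asked.** Recording SAEs and TEAEs, and reviewing key symptoms, are listed procedures at Days 15 and 29, Section 8.3.2 calls for careful monitoring, and CRF guidance is not available here. But the visit lists do not say how events are to be elicited, and the one sentence that does names only observation and volunteering.

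**Much of safety is little exposed.** This also stands. Vital status and re-admissions are followed to Day 90. Chemistry and hematology fall on Days 5, 15 and 29 whether or not the subject is discharged. Vital signs cover each infusion and 2 hours after it. Anticipated COVID-19 symptoms are generally not recorded as TEAEs in either setting.

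**The artefact is small beside the noise.** At about 50 per arm and an assumed rate of 50%, the 95% half-width of a risk difference is 1.96 × √(2 × 0.25/50), about 20 points. True, but a directional bias linked to efficacy is not cured by imprecision, and it is cheap to reduce.

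**Fewer events after earlier discharge may be real**, through less severe illness, less hospital care or no second infusion. This stands. The plan as written could not separate that from under-detection.

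**Conclusion.** The point holds as a risk of differential ascertainment, not as a demonstrated bias. The passive rule, the fall in contact at discharge and the unadjusted summaries are all in the documents. A reader might infer that the arm discharged sooner will show fewer events. The documents do not support that: it needs both a between-arm difference in discharge timing and lower detection at home, and they give neither. With equal discharge timing, or q = 1, the artefact is nil.

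Under the assumptions above it reaches about 9 points at the extreme (R = 70%, q = 0.3, Day 6 v 12). It is 4 points or less in 28 of the 36 scenarios, and smaller still if events cluster early. It concerns mainly non-serious, between-visit events. It merits a cheap correction and a caveat on the TEAE comparison; it does not undermine the safety evaluation as a whole.

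**What to change.** 1. **Protocol 8.3.8.** Replace the passive sentence with collection by observation, by spontaneous report, and by one standard non-leading question on how the subject has been over the whole interval since the last contact. Ask it at every scheduled contact: daily in hospital, Days 5, 15 and 29, any Day 8 infusion visit, and both phone checks. Carry it into the CRF guidance.
2. **SAP 7.2.5.** Add a supportive by-arm table of TEAEs with onset from the first infusion through Day 4. Day 4 is the earliest permitted day of the mandatory Day 5 ± 1 visit, so a window ending on Day 5 would not be covered for every subject. State that the table does not cover the second infusion.
3. **Protocol 4.2 and Appendix 1, footnote l.** Reconcile them on whether subjects discharged before Day 5 are followed daily through Day 5 or only seen at the Day 5 visit.

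The cost is a few lines in the protocol and CRF guidance and one extra table, with no new visits. Somewhat more non-serious AEs will be recorded. Contact remains more frequent in hospital, so the question reduces the effect of unequal contact without removing it.
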